Study Imaging	18F-fluciclovine PET-MRI in combination with multiparametric prostate MRI using high resolution DWI
Control Imaging	Standard multiparametric prostate MRI
Reference standard	MRI-targeted prostate biopsies will serve as the reference standard and all lesions seen on any MRI protocol will be biopsied.
Statistical analysis	Our hypothesis is that 35% of biopsy-proven tumors will be detected on PET-hrMRI and not on standard MRI. If we assume that no biopsy proven tumors will only be detected on standard MRI, at $\alpha=0.05$, $n=20$ provides a power of 80%.

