We herein propose a prospective trial to evaluate the effectiveness of 18F-fluciclovine PET-hrMRI versus standard mpMRI at identifying prostate cancer targets for HIFU therapy. Patients with clinically localized, unilateral high grade prostate cancer (Gleason score 7-10 prostate cancer localized to one lobe on prior biopsies) OR at high risk for having unrecognized high grade prostate cancer (overall Gleason score 6 with \geq half of systematic biopsy cores positive and \geq 50% of core involvement in at least one core), interested in HIFU would receive both a standard mpMRI and 18F-fluciclovine PET-hrMRI. They would then undergo a mapping biopsy using a standard sextant template plus MRI/US-fusion targeted biopsy of any suspicious lesion on mpMRI or PET-hrMRI. The primary endpoint would assess the number of biopsy-proven cancers that mpMRI would have missed compared with PET-hrMRI. Following our tumor mapping study, patients with high grade disease (i.e. Gleason grade 4 or 5) in one lobe undergo hemigland or focal HIFU of that lobe. At 6 months, patients would undergo repeat prostate biopsy to assess the negative biopsy rate in the treated region and absence of Gleason grade 4 or 5 in the untreated region as secondary endpoints.

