3.1 Overview

This prospective trial will evaluate the effectiveness of 18F-fluciclovine PET-hrMRI versus standard mpMRI at identifying prostate cancer targets for HIFU therapy. Patients with clinically localized, Gleason score 7-10 prostate cancer localized to one lobe on prior biopsies or overall Gleason score 6 with \geq half of systematic biopsy cores positive and \geq 50% of core involvement in at least one core, interested in HIFU would receive both a standard mpMRI and 18F-fluciclovine PET-hrMRI. They would then undergo a mapping biopsy using a standard sextant template plus MR/US-fusion targeted biopsy of any lesions with PI-RADS scores \geq 3 on hrMRI or 18F-fluciclovine PET positivity. The primary endpoint would assess the number of biopsy-proven cancers that mpMRI would have missed compared with hrMRI and/or 18F-fluciclovine PET. Following our tumor mapping study, patients with high grade disease (i.e. Gleason grade 4 or 5) in one lobe undergo hemigland or focal HIFU of that lobe. At 6 months, patients would undergo repeat mpMRI and prostate biopsy (MR/US-fusion biopsy plus standard sextant biopsy) to assess the negative biopsy rate in the treated region and absence of Gleason grade 4 or 5 in the untreated region as secondary endpoints

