3.4.2 Study Calendar

Procedure	Screening	Imaging	Post-imaging²	Standard of Care (SOC) Treatment	Post SOC Treatment 6 months (+/- 1.5 months) following HIFU
Informed Consent/Registration	X				
Demographics/Medical History	X				
Prior and Current Medication Review	X				
Vital Signs ⁵	X				
Physical Exam ⁵	X				
Symptoms Assessment	X				
Standard MRI		X (at least one day prior to targeted prostate biopsy)			X (at least one day prior to targeted prostate biopsy)
			X		X

Tissue collection ⁴					
18-fluciclovine PET-hrMRI		X (at least one day prior to targeted prostate biopsy)			
Adverse Event Review ⁶		X	X	X	X
Hemigland or Focal HIFU ¹				X (performed within 4 months after mapping and/or targeted prostate biopsy)	
Standard Sextant Mapping Biopsy			X		X
MR/US-fusion targeted biopsy			X ³		X

1. Focal HIFU performed on study for patients with confirmed unilateral high grade prostate cancer.
2. End of study for bilateral Gleason ≥ 7 disease
3. Of any lesions with PI-RADS scores ≥ 3 on hr MRI or 18F-fluciclovine PET positivity
4. Tissue collection includes left over tissue from standard of care collection only.
5. Do not need to be repeated if obtained within 90 days of screening.
6. Only grade 3 and above imaging-related AEs will be captured and all SAEs following the receipt of fluciclovine F18.

Pre-HIFU Imaging Protocol for Tumor Mapping

Eligible participants will then undergo mapping MRI in advance of HIFU therapy using both standard mpMRI and PET-hrMRI. All imaging will be completed in one sitting. hrMRI increases the length of the MRI by approximately 5 minutes. PET-MRI sequences increased the length of mpMRI by 30 minutes. Scanning will be done on the Siemens Biograph mMR scanner at the Research Imaging Core facility in the Davis Building.

Subjects undergoing a PET-hrMRI will be screened using the standard clinical protocol to determine whether it is safe to administer contrast to the subject.

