PET scans involve injection of a radioisotope. Subjects undergoing a contrast-enhanced MR-PET will be screened using the standard clinical protocol to determine whether it is safe to administer contrast to the subject. An IV line will be inserted, and the participant will receive 10 mCi $\pm 20\%$ 18F-fluciclovine injection diluted up to 10mL injected via the IV, as an IV bolus injection followed by 10mL flush with normal saline solution. The participant will then be positioned supine in the scanner and will be scanned in the area of the prostate. The research PET scan will be a dynamic list mode scan. Meaning the PET would start first, then 18F fluciclovine would be injected immediately after the scan is started. For the PET acquisition, participants will be imaged for approximately 30 minutes.

All MRI images will be read according to PI-RADS (version 2) by a dedicated GU radiologists who has experience reading over 500 prostate MRIs. All PET scans will be

read by nuclear medicine co-investigators on the study ([name]). All lesions with PI-RADS greater than or equal to 3 and all PET positive areas will be considered suspicious for cancer. A region of interest (ROI) application will be used. The circumference of a suspicious lesion will be drawn on each individual MRI slice. The lesion volume and average ADC will be calculated from the ROI's. The tumor volumes and ADCs will be provided by the radiologist. To prevent the hrMRI from influencing the review of the mpMRI, all mpMRI's will be reviewed first. The radiologist will always be blinded to previous pathology.

Mapping Biopsy Protocols

After the pre-HIFU imaging protocol for tumor mapping, all patients will undergo a transrectal ultrasound-guided targeted mapping biopsy. The biopsy will include a standard sextant template plus MR/US-fusion targeted biopsy of any lesions with PI-RADS scores ≥ 3 on hrMRI or 18F-fluciclovine PET positivity. These areas will be targeted using the UroNav targeting software platform. As an exploratory analysis, remnant formalin-fixed paraffin embedded tumor tissue will be requested for RNAseq transcriptome analysis of lesions that are positive on mapping biopsy.

Eligibility for HIFU

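### The documents give two conflicting rules for which lesions get targeted cores; the narrower one verifies mpMRI-only cancers less completely and tilts the sensitivity comparison toward PET-hrMRI

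*Combined protocol and SAP*

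**What the plan says.** Two places include lesions seen on standard mpMRI:

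- Study Summary, Reference standard: "MRI-targeted prostate biopsies will serve as the reference standard and all lesions seen on any MRI protocol will be biopsied".
- Section 1.0, Study Abstract: "MRI/US-fusion targeted biopsy of any suspicious lesion on mpMRI or PET-hrMRI".

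Three places name only hrMRI and PET:

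- Section 3.1, Overview: targets are PI-RADS scores of at least "3 on hrMRI or 18F-fluciclovine PET positivity. The primary endpoint would assess the number of biopsy-proven cancers" that mpMRI would have missed.
- Section 3.4.2, calendar footnote 3: "Of any lesions with PI-RADS scores ≥ 3 on hr MRI or 18F-fluciclovine PET positivity".
- Section 3.4.2, Mapping Biopsy Protocols: a sextant template for everyone plus "MR/US-fusion targeted biopsy of any lesions with PI-RADS scores ≥ 3 on hrMRI or 18F-fluciclovine PET positivity".

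Other passages lean toward the broad rule without settling it. Section 3.4.2 describes "mapping MRI in advance of HIFU therapy using both standard mpMRI and PET-hrMRI" and treats any PI-RADS 3 or higher lesion as suspicious without naming a scan. Section 4.0 sends mapping results to the physicians who use them for the biopsy. Section 6.0 says every area of concern is biopsied but does not define the term.

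Section 6.0 reads the primary endpoint as a comparison of sensitivities with biopsy-proven cancer as gold standard. The power statement in the Study Summary adds: "If we assume that no biopsy proven tumors will only be detected on standard MRI".

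**The concern.** For a lesion positive on standard mpMRI only, the Study Summary and Abstract require targeted cores and the three procedural passages do not provide for them. Staff will work from the calendar and the biopsy procedure, so the narrow wording could well be what is done.

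Sensitivity is computed among proven cancers, so a cancer that is not proven leaves the analysis. Under the narrow rule the loss falls on one discordant cell only, the cancers that mpMRI saw and PET-hrMRI did not. Section 2.7 itself reports that targeted fusion biopsy improves on the sensitivity of sextant biopsy by 24%, so sextant cores are not an equal substitute. The planning assumption that this cell is empty would also become partly self-fulfilling, because the design would seldom prove such a tumour.

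**Working it through.** **The plan's own figures.** Take p10 as the share of cancers seen only on PET-hrMRI and p01 as the share seen only on mpMRI. The two-sided asymptotic McNemar sample size is

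n = [1.96·√(p10+p01) + 0.8416·√(p10+p01−(p10−p01)²)]² / (p10−p01)².

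With the Study Summary's p10 = 0.35 and p01 = 0, n = 19.9, and power at n = 20 is 80.3%. The stated 80% reproduces.

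**Anchors for p01.** The documents give no value other than the assumed zero.

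- *Implied by Section 6.0.* Take the Section 2.5 pilot sensitivities, 22/23 and 14/23, with r3 = 0.15. Then p11 = (22/23)(14/23) + 0.15·√[(22/23)(1/23)(14/23)(9/23)] = 0.597, so p10 = 0.957 − 0.597 = 0.359 and p01 = 0.609 − 0.597 = 0.0115. The formula then gives n = 21.5, matching the stated 22 single-lesion patients. That the plan used these sensitivities is an inference.
- *Pilot ceiling.* hrMRI missed 1 of 23 positive zones, so at most 1/23 = 4.35% could have been mpMRI-only.

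**Bias in the difference.** Let s be the share of mpMRI-only cancers that sextant cores confirm (also not given, so a range), with all other cells held as verified.

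- True difference: p10 − p01.
- Observed difference: D(s) = (p10 − s·p01) / (1 − (1−s)·p01).
- The derivative of D in s has numerator −p01·(1 − p01 + p10). This is negative whenever p01 > 0, so incomplete capture always widens the difference in favour of PET-hrMRI.

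With p10 = 0.35, in percentage points:

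| p01 | True (s = 1) | s = 0.5 | s = 0 |
|---|---|---|---|
| 1.1% | 33.9 | 34.6 | 35.4 |
| 4.35% | 30.7 | 33.6 | 36.6 |
| 5% | 30.0 | 33.3 | 36.8 |

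The s = 0 column is a bound, not an expected case.

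**Effect on the test.** Simulation with 200,000 runs per cell: 20 patients, 65% with one lesion and 35% with two (mean 1.35), latent-normal within-patient correlation 0.1. The statistic is T = (Σd_k)²/Σd_k² with critical value 3.84, counting only results that favour PET-hrMRI. Ranges cover two versions of d_k: the patient's discordant difference, and that difference divided by the patient's verified lesion count.

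| Scenario | s = 1 | s = 0.5 | s = 0 |
|---|---|---|---|
| p10 = 35%, p01 = 1.1% | 92% | 95% | 97–98% |
| p10 = 35%, p01 = 4.35% | 74% | 86–87% | 97–98% |
| Equal, 4.35% each way | 0.3–0.9% | 0.5–1.5% | 0.8–2.4% |
| Equal, 10% each way | 1.7–2.3% | 5–8% | 13–24% |
| Equal, 15% each way | 2.1–2.3% | 9–10% | 38–52% |

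The first two rows are not false positives, since a true gain exists; they show overstated certainty. They exceed the plan's 80% for two reasons. The simulation has 20 × 1.35 = 27 lesions on average. Also, the uncorrected test rejects more often than the asymptotic formula predicts when no mpMRI-only lesion is recorded: for 20 single lesions at p10 = 0.35 it needs only 4 discordant lesions, with probability 95.6%, against 75.5% for the exact two-sided test, which needs 6.

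The equal-sensitivity rows also depend on the test. For 20 single-lesion patients at 15% each way and s = 0, P(Bin(20, 0.15) ≥ 4) = 35.2% uncorrected, and P(Bin(20, 0.15) ≥ 6) = 6.7% exact.

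**The case against.** The strongest reply is that the narrow wording is shorthand. The procedure says what the biopsy will include, not what it is limited to. The one entry labelled as the reference standard is explicit, and the passages on suspicious lesions, mapping MRI and areas of concern all point the same way. This is a plausible reading, but footnote 3 repeats the same trigger and Section 3.1 repeats it again, so a reader cannot tell which rule governs.

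The second reply is that the affected cell may be almost empty, and it carries real weight. The study imaging is "18F-fluciclovine PET-MRI in combination with multiparametric prostate MRI using high resolution DWI", so it is itself a multiparametric MRI with PET added. mpMRI is read first, Section 9.0 records a change to one radiologist, and nothing blinds the hrMRI read to the mpMRI read, so a lesion called on mpMRI may be carried over and targeted anyway. The pilot's p = 0.004 fits 8 versus 0 discordant zones (one-sided exact 0.0039) better than 9 versus 1 (0.011), which points toward p01 = 0. Against that, 0 of 23 still has an exact 95% upper limit of 14.8%, and 1 of 23 has 21.9%, ignoring clustering.

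Third, the equal-sensitivity scenarios at 10–15% lie well above the pilot ceiling and run against the pilot's 95.7% versus 60.9%. That is right: they show where the false-superiority rate would become serious, not what is expected.

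Finally, the Section 3.3 endpoint, the count of cancers that standard imaging missed, is unaffected because those lesions are targeted under either rule. That also stands.

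**Conclusion.** The contradiction is real, and so is the direction of bias if the procedural text is followed; confidence in both is high. Confidence in the size is low, because it rests on assumed values of p01 and s. With p10 = 0.35, and from half to none of the mpMRI-only cancers captured, the sensitivity difference is overstated by 0.7 to 1.5 points at p01 = 1.1%, by 2.9 to 5.9 points at 4.35%, and by 3.3 to 6.8 points at 5%. At 4.35% the chance of a significant result rises from 74% to 86–98%. False superiority clearly exceeds the nominal one-sided 2.5% only at about 10–15% discordance each way. The bias is zero if p01 = 0 or if the Study Summary rule is what is done. The likely effect is modest, but it falls on the primary test and interval of a 20-patient study, and the assumption of no mpMRI-only tumours could not be fairly checked.

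**What to change.** Reconcile the Study Summary, Section 1.0, Section 3.1, Section 3.4.2 (footnote 3 and Mapping Biopsy Protocols) and Section 6.0 into one target rule that verifies both modalities equally, as the Study Summary and Abstract already commit to. Report the number of proven cancers seen only on mpMRI.

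If the narrower wording is kept, present the sensitivity difference, its test and its interval as subject to differential verification, and treat the Section 3.3 missed-cancer count (the incremental yield of PET-hrMRI) as the interpretable result.

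The cost is protocol wording. mpMRI is already read before hrMRI, so its lesion list exists before biopsy. The downside is possibly a few more targeted cores in the same session, which the Study Summary and Abstract already promise.

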3.5 Removal of Subjects from study

Patients can be taken off the study at any time at their own request, or they may be withdrawn at the discretion of the investigator for safety, behavioral or administrative reasons. The reason(s) for discontinuation will be documented and may include:

- 3.5.1 Patient voluntarily withdraws (follow-up permitted);
- 3.5.2 Patient withdraws consent (discontinue all study procedures and follow-up)
- 3.5.3 Patient is unable to comply with protocol requirements;
- 3.5.4 Treating physician determines continuation on the study would not be in the patient's best interest;
- 3.5.5 Lost to follow-up. If a research subject cannot be located in order to obtaining data to inform the primary or secondary endpoint, the subject may be considered "lost to follow-up." All attempts to contact the subject during the two years must be documented.

4.0 Study Risks

All agents administered to patients and all invasive procedures used in this study are approved by the U.S. Food and Drug Administration. This study investigates a novel software-based MRI imaging protocol that improves image resolution, and it investigates the off-label use of F18 fluciclovine for prostate PET-MRI.

F18 fluciclovine is currently approved for PET-CT for men with suspected prostate cancer metastasis. MR/ultrasound fusion biopsies and HIFU for prostate ablation are also approved procedures that are being routine performed as standard-of-care. All invasive procedures will therefore be performed following standard informed consent.

Magnetic Resonance Imaging (MRI)

MRI imaging is among the least invasive of all imaging modalities. The U.S. Food and Drug Administration has labeled MR systems of up to 4.0 Tesla as having "non-significant risk" and currently there is no evidence that MR imaging causes any long-term or irreversible effects in human beings. However, there are certain risks, which are detailed below.

MRI imaging utilizes magnetic fields and radiofrequency fields, both of which can be harmful in certain situations. Magnetic fields can cause ferromagnetic implants or ferromagnetic foreign bodies, such as intracranial aneurysm clips, shrapnel, and intraocular metal chips to become dislodged and tear the surrounding soft tissue. Therefore, MRI imaging is contraindicated in persons with ferromagnetic implants or ferromagnetic foreign bodies. It is also contraindicated in persons with electrically, magnetically or mechanically activated implants because the magnetic field can cause these to function erratically. In addition, persons wearing metallic objects may be at danger for them becoming dangerous projectiles, due to them inadvertently becoming introduced into the magnetic field. All subjects will be prescreened carefully and all

scanners are used in accordance with guidelines set by the Bureau of Radiological Health.

Fluciclovine F18 (Axumin)

The recommended dose is 370 MBq (10 mCi) administered as an intravenous bolus injection. The (radiation absorbed) effective dose resulting from this dose of Axumin is 8 mSv. The clinical trial database for Axumin includes data from 877 subjects including 797 males diagnosed with prostate cancer. Most patients received a single administration of Axumin, a small number of subjects (n = 50) received up to five administrations of the drug. The mean administered activity was 370 MBq (range, 163 to 485 MBq). Adverse reactions were reported in ≤1% of subjects during clinical studies with Axumin. The most common adverse reactions were injection site pain, injection site erythema and dysgeusia.

Hypersensitivity to Medications - Occasionally, people have allergic reactions when taking any medication. Subjects may receive medications such as contrast. Hypersensitivity reactions may include symptoms such as shortness of breath, wheezing, flushing, nasal congestion and skin rash. In most cases, initial symptoms occur within minutes of drug administration and quickly reverse themselves or resolve with prompt medical treatment.

In general, allergic reactions to medicines are more likely to occur in people who have allergies to other drugs, foods, or things in the environment. Subjects will be asked about any pre-existing allergies before administering any medications during the study.

Incidental Findings

Only noted clinically significant incidental findings will be communicated to the subject, per CSMC IRB and Legal Department approved policy, as a result of agreeing to undergo a research MRI scan. No reports or images will be provided to subjects and their medical records. However, MRI mapping results will be provided to the treating physicians who will use this information for MR/ultrasound guided prostate biopsy.

5.0 ADVERSE EVENTS (AE)

5.1 Definitions

5.1.1 Adverse Event: An adverse event is any untoward medical occurrence in a patient receiving study intervention and which does not necessarily have a causal relationship with this intervention. An AE can therefore be any unfavorable and unintended sign (including an abnormal laboratory finding), symptom, or

disease temporally associated with the use of an experimental intervention, whether or not related to the intervention.

5.1.2 Serious Adverse Events (SAE): A “serious” adverse event is defined in regulatory terminology as any untoward medical occurrence that:

- Results in death. If death results from (progression of) the disease, the disease should be reported as event (SAE) itself.
- Is life-threatening.
(the patient was at risk of death at the time of the event; it does not refer to an event that hypothetically might have caused death if it were more severe).
- Requires in-patient hospitalization or prolongation of existing hospitalization for ≥ 24 hours.
- Results in persistent or significant disability or incapacity
- Is a congenital anomaly/birth defect
- Is an important medical event

Any event that does not meet the above criteria, but that in the judgment of the investigator jeopardizes the patient, may be considered for reporting as a serious adverse event. The event may require medical or surgical intervention to prevent one of the outcomes listed in the definition of “Serious Adverse Event“.

Step 1: Identify the type of adverse event using the NCI Common Terminology Criteria for Adverse Events (CTCAE v4).

Step 2: Grade the adverse event using the NCI CTCAE v4.

Step 3: Determine whether the adverse event is related to the protocol therapy Attribution categories are as follows:

- Definite – The AE is clearly related to the study treatment.
- Probable – The AE is likely related to the study treatment.
- Possible – The AE may be related to the study treatment.
- Unlikely – The AE is doubtfully related to the study treatment.
- Unrelated – The AE is clearly NOT related to the study treatment.

Note: This includes all events that occur within 30 days of the last dose of protocol treatment. Any event that occurs more than 30 days after the last dose of treatment and is attributed (possibly, probably, or definitely) to the agent(s) must also be reported accordingly.

Step 4: Determine the prior experience of the adverse event.

Expected events are those that have been previously identified as resulting from administration of the agent. An adverse event is considered unexpected, for expedited reporting purposes only, when either the type of event or the severity of the event is not listed in:

- the current known adverse events listed in section 1.4
- the drug package insert
- the current Investigator's Brochure

5.1.3 Unanticipated Problem (UP)

Unanticipated problems include any incident, experience, or outcome that meets all of the following criteria:

- Unexpected (in terms of nature, severity, frequency) given (a) the research procedures that are described in the protocol-related documents, such as the IRB-approved research protocol and informed consent document; and (b) the characteristics of the subject population being studied;
- Related or possibly related to participation in the research (possibly related means there is a reasonable possibility that the incident, experience, or outcome may have been caused by the procedures involved in the research); and
- Suggests that the research places subjects or others at a greater risk of harm (including physical, psychological, economic, or social harm) than was previously known to an individual or group of individuals (including research subjects, research staff, or others not directly involved in the research).

